Clinical Study:

A PROSPECTIVE, OPEN, MULTICENTRE CLINICAL TRIAL WITH
ONE COHORT ANALYSING THE EFFICACY AND SAFETY OF
MINIJECT IN PATIENTS WITH OPEN ANGLE GLAUCOMA
UNCONTROLLED BY TOPICAL HYPOTENSIVE MEDICATIONS
(ISM04)

ClinicalTrials.gov identifier:

NCT03193736

Date of the document:

17Jul2017

Clinical Investigational Plan

A PROSPECTIVE, OPEN, MULTICENTRE CLINICAL TRIAL WITH ONE COHORT ANALYSING THE EFFICACY AND SAFETY OF MINIJECT IN PATIENTS WITH OPEN ANGLE GLAUCOMA UNCONTROLLED BY TOPICAL HYPOTENSIVE MEDICATIONS

Synopsis

according to EN ISO 14155:2011

Medical Device Name:	MINIject
Clinical Trial Identifier:	ISM04
CIP Version:	Version 3.0
Release date	17-JUL-2017

This document includes confidential and privileged information and data that contain trade secrets which are property of iSTAR Medical. This information must not be made public without prior written permission of iSTAR Medical. This document may be disclosed to and used by the staff that conducts the clinical trial at a clinical investigational site.

Synopsis

Acronym	MINIject Study
Title	A prospective, open, multicenter clinical trial with one cohort analyzing the efficacy and safety of MINIject in patients with open angle glaucoma uncontrolled by topical hypotensive medications
Sponsor	iSTAR Medical S.A. [name]
Ethical Aspects	
Glaucoma is a complicated disease in which damage to optic nerve leads to progressive, irreversible vision loss. Glaucoma is the second leading cause of blindness. Glaucoma can be treated with eye drops, pills, laser surgery, traditional surgery or a combination of these methods. The goal of any treatment is to prevent loss of vision by lowering the IOP because vision loss from glaucoma is irreversible.
 
If a surgery is needed the currently available options (trabeculectomy, available implants) do not promise a long-term effect and new devices are requested. STARflo MINIject is a promising new developed glaucoma device with a new structure and unique working method.

Study purpose	The aim of this study is to assess the efficacy and safety of the MINIject system in patients diagnosed with open angle glaucoma uncontrolled by topical hypotensive medications.
Investigational Device and procedure	
MINIject is an integrated system comprising a minimally-invasive Glaucoma Drainage Implant and a Delivery Tool.
 
The Delivery Tool is configured for inserting the implant into the sub-scleral location through an ab-interno minimally-invasive approach. It is single-use.
 
Device options to be evaluated in this study:
 
Implant CS 600 with Curved Shaft.
 
Intervention:
 
The intervention is to be performed stand-alone.

Indication	
MINIject is indicated in adult, male and female patients diagnosed with open angle glaucoma, and where the progression of glaucoma is not adequately controlled by topical hypotensive medications.
 
MINIject is intended to be used to reduce the intraocular pressure (IOP) by channeling aqueous humor out of the anterior chamber to a sub-scleral location, thus enhancing the physiological uveoscleral outflow.

Synopsis

Design

Baseline and evaluation time points:

Screening / Baseline	Follow-up 1 day / 1 week / 2 weeks / 1 Month / 3 Months	Follow-up 6 / 12 / 18 / 24 Months
patient inclusion	Safety evaluation	safety and efficacy evaluation
medicated diurnal IOP baseline	single point IOP measurement	medicated diurnal IOP

This prospective, non-comparative, open, multi-center, interventional clinical investigation is designed as one cohort study and intended to show the efficacy and safety of the MINIject system consisting of the CS 600 MINIject implant and the delivery tool with curved shaft.

In total 25 patients will be enrolled in approximately 5 sites in Panama, India and Europe (France or Germany).

The study will evaluate the efficacy and safety of the implant and IOP lowering effects with or without glaucoma medications. The procedure will be a stand-alone surgery. Overall, the patient will be asked to attend at 10 visits and perform several examinations up to 24 months after surgery.

The primary efficacy objective of the present study is to show the IOP reduction under medication 6 months after surgery compared to medicated diurnal IOP at screening.

The sponsor will evaluate the ease of use of the delivery tool based on questionnaires completed by the surgeons after surgery.

Primary study objective

The primary objective is to show a reduction in medicated diurnal IOP between screening/baseline visit and medicated diurnal IOP at 6 months after surgery.

Secondary study objectives

To test the reduction in medicated diurnal IOP between screening/baseline visit and medicated diurnal IOP 12 months and 24 months after surgery.

To assess the safety of the MINIject in terms of nature and severity of Adverse Events (AE/SAE), Adverse Device Effects (ADE/SADE) and Unanticipated Adverse Device Effect (UADE)*.

To assess the rate of peripheral and central corneal endothelial cells density-loss.

To assess the rate defined as:

- Complete success: diurnal IOP \leq 21mmHg and $>$ 5mmHg with a minimum 20% diurnal IOP reduction from baseline without the need for glaucoma hypotensive medication.
- Qualified success: diurnal IOP \leq 21mmHg and $>$ 5mmHg with a minimum 20% diurnal IOP reduction from baseline with the concomitant use of glaucoma hypotensive medication.

To assess the reduction of the number of hypotensive active ingredients compared to screening visit.

Synopsis

* referring to expected AEs for implantable glaucoma devices as listed in ANSI Z80.27.2014 and FDA Guidance Premarket Studies of Implantable Minimally Invasive Glaucoma surgical (MIGS) Devices.

Assessed Parameter	The assessed parameters are listed in detail in Table 1 at the end of this synopsis.
Patient selection	
Inclusion criteria
 
Any patient is eligible for inclusion in this clinical investigation if all of the following criteria apply:
 
Males or females, 18 years of age or older.
 
Diagnosis of primary or secondary open angle glaucoma during screening/baseline visit or earlier.
 
Grade 3 (open, 20-35 degrees) or grade 4 (wide open, 35-45 degrees) according to Shaffer Angle Grading System.
 
Glaucoma not adequately controlled by one to four different topical hypotensive medication(s), given each for at least one month, as confirmed by $21 \text{ mmHg} \leq \text{IOP} \leq 35 \text{ mmHg}$ in the study eye at screening and baseline visits.
 
Patient must be willing and able to return for scheduled study-related examinations.
 
Patient must provide written informed consent.
 
Exclusion criteria
 
Any patient is not eligible for inclusion in this clinical investigation if one or more of the following criteria apply:
 
Diagnosis of glaucoma other than open angle glaucoma (e.g. angle closure glaucoma) in the study eye.
 
Grade 2 (narrow, 20 degrees), grade 1 (extremely narrow, less or equal to 10 degrees) and grade 0 (closed or slit) according to Shaffer Angle Grading System.
 
Neovascular glaucoma in the study eye.
 
Corneal opacity or iridocorneal angle not visible through gonioprism in the study eye, preventing correct placement of the implant.
 
Prior glaucoma surgery in the study eye, patient treated with argon laser trabeculoplasty or selective laser trabeculoplasty in the study eye may be eligible if treatment performed ≥ 90 days before screening visit.
 
Visual field defect in the 10 degree central field in the study eye.
 
Anticipated need for ocular surgery or retinal laser procedure in the study eye in the 12 months following surgery.
 
Anterior chamber anatomic configuration of high risk for development of angle closure glaucoma in the study eye.

Synopsis

Clinically significant corneal disease (e.g., corneal dystrophy) in the study eye.

Pre-existing ocular or systemic pathology that, in the opinion of the physician, is likely to cause postoperative complications following implantation of the device in the study eye.

Evidence of crystalline lens subluxation or luxation in the study eye.

Evidence of vitreous loss in the anterior chamber in the study eye.

Clinically significant intra-ocular inflammation or infection, presence of ocular disease such as uveitis, ocular infection, severe dry eye, severe blepharitis, active proliferative/inflammatory retinopathy in the study eye.

Presence of silicone oil in the study eye.

Patients treated with systemic acetazolamide within 3 days before screening visit.

Patients with poor vision (LogMar score: +1.0) in non-study eye, unless there is an expected benefit for the study eye, in the opinion of the investigator.

Participation in any study involving an investigational drug or device within the past 3 Months.

Only for women of childbearing potential: positive urine pregnancy test at screening.

Individuals under tutorship or trusteeship.

Quality Assurance	During the clinical investigation, the sites will be visited by CRO staff to review the progress of the clinical investigation, review the data collected, conduct source data verification, (according to ISO 14155:2011(E); define the extend of source data verification) perform device accountability, identify issues and address their resolution. The aim of the monitoring of the clinical investigation is to ensure that the data collected is authentic, accurate and complete, to ensure the safety of the subjects and that the subject's rights are protected, and to ensure that the clinical investigation is performed according to the approved clinical investigation plan and all applicable regulations and guidelines.
--------------------------	---

Sample Size	Sample size is obtained by a paired sample t-test, 2-sided, with alpha of 0.05 and power of 0.9. The difference of interest is taken equal to 5.2 mmHg. Under the conservative assumption that 25% of subjects will drop out of the study, this treatment effect will be reduced to $0.75*5.2 = 3.9$ mmHg if all patients are included in an ITT analysis. The variance of the difference in IOP between the month 6 visit and baseline is assumed to be at most equal to $3^2+5^2=34$, hence the standard deviation is taken equal to 5.83. Under these assumptions, the sample size required is equal to 25 patients.
--------------------	--

Statistical rationale for sample	An IOP reduction $\geq 20\%$ has been previously used as success criterion and thus can be defined as clinically meaningful.
---	--

Synopsis

size calculation

The mean baseline IOP of $26.0 \text{ mmHg} \pm 3.0$ used for calculation is derived from published study results involving comparable study population; subjects with OAG uncontrolled by medication(s).

The mean IOP at 6 months is estimated to $20.8 \text{ mmHg} \pm 5$, the standard deviation is derived from published study results involving comparable devices.

Based on these assumptions, the estimated sample size of 25, in order to obtain 16 completed subjects at 6 Months follow-up (endpoint for the primary objective).

Synopsis

FLOW CHART

	Visit 0	Visit 1	Visit 2	Visit 3	Visit 4	Visit 5	Visit 6	Visit 7	Visit 8	Visit 9	Visit 10
	Screen/ Baseline	Surgery	1 Day	1 week	2 weeks	1 Month Safety evaluation	3 Months	6 Months Safety & Efficacy evaluation	12 Months Safety & Efficacy evaluation	18 Months Safety & Efficacy evaluation	24 Months Safety & Efficacy evaluation
GENERAL ASSESSMENTS	Day - 42 to -1	Day 0	Day 1	Day 5-9	Day 12-16	Day 21-35	Day 70-98	Day 168-196	Day 335-425	Day 510-600	Day 700-790
Signed informed consent	X										
Demography/ relevant medical and ocular history/Glaucoma diagnosis	X										
Inclusion /exclusion criteria	X										
Urine pregnancy test (women of childbearing potential only)	X										
Concomitant ocular & non-ocular medications,	X	X	X	X	X	X	X	X	X	X	X
AE/SAE recording	X	X	X	X	X	X	X	X	X	x	X
Implantation		X									
Implant position assess by investigator's judgment		X									
Record video of surgery		X									
Ease of use feedback questionnaires completed by investigator		X									
QOL questionnaire, CIGTS sub-part	X							X	X	X	X

Synopsis

	Visit 0	Visit 1	Visit 2	Visit 3	Visit 4	Visit 5	Visit 6	Visit 7	Visit 8	Visit 9	Visit 10
OCULAR ASSESSMENTS	Screening/ Baseline	Surgery	1 day	1 week	2 weeks	1 Month Safety evaluation	3 Months	6 Months Safety & Efficacy evaluation	12 Months Safety & Efficacy evaluation	18 Months Safety & Efficacy evaluation	24 Months Safety & Efficacy evaluation
	Day -42 to -1	Day 0	Day 1	Day 5-9	Day 12-16	Day 21-35	Day 70-98	Day 168-196	Day 335-425	Day 510-600	Day 700-790
	BCVA	X		X	X	X	X	X	X	x	X
IOP, Goldmann Appl. Tonometry, diurnal (8:00 AM, 12:00 AM, 4:00 PM)	X							X	X	x	X
IOP (Single time point)			X	X	X	X	X				
Visual field testing (Octopus or Humphrey)	X					X	X	X	X	x	X
Optic disc photograph of the optic nerve	x					x	x	x	x	x	x
Vertical C/D ratio	X					X	X	X	X	x	X
Central corneal thickness (pachymetry)	X							X	X	x	X
Gonioscopy, angle grading using Shaffer grading	X										
Recording Gonioscopy image		X				X					
Slit lamp examination	X		X	X	X	X	X	X	X	x	X
Dilated fundus examination	X		X	X		X		X	X	x	X
Peripheral and central specular microscopy	X							X	X	x	X
Eye symptoms	X		X	X	X	X	X	X	X	x	X
Assess Implant position (UBM)				X				X	X	x	X

Table 1: Flow chart for cohort, general and ocular assessments. All ocular assessments (except BCVA) are to be done on study eye only, except at screening visit, where the assessments are to be done on both eyes.

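### Does the 21-35 mmHg entry rule, which names two pre-operative visits where one is scheduled and reuses the qualifying IOP as baseline, require a change to the plan?

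*Combined protocol and SAP*

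**What the plan says.** In the Synopsis, under Patient selection, the IOP criterion (21 to 35 mmHg on one to four topical medications) applies "in the study eye at screening and baseline visits". Another item in the same list treats this as one occasion: "Diagnosis of primary or secondary open angle glaucoma during screening/baseline visit or earlier". The Design table has a single Screening / Baseline column, which serves for both inclusion and the diurnal baseline. The Flow chart has one assessment visit before surgery, Visit 0 (Day -42 to -1), with diurnal Goldmann tonometry at three clock times. Single-point IOP is marked only from Visit 2 to Visit 6. On attendance, the Design section states: "Overall, the patient will be asked to attend at 10 visits".

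The Design section sets the 6-month IOP against baseline as "compared to medicated diurnal IOP at screening". The primary objective reads: "The primary objective is to show a reduction in medicated diurnal IOP between screening/baseline visit and medicated diurnal IOP at 6 months after surgery". The success rates use the same reference, for example "with a minimum 20% diurnal IOP reduction from baseline without the need for glaucoma hypotensive medication". The study has one cohort and no control. On size: "Sample size is obtained by a paired sample t-test, 2-sided, with alpha of 0.05 and power of 0.9". The baseline of 26.0 ± 3.0 mmHg is "derived from published study results involving comparable study population".

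**The concern.** Three things look wrong.

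- **Visits.** The criterion names two occasions and the schedule provides one, so a site might not know whether a second qualifying measurement is needed.
- **Reading.** The criterion says only IOP, and Visit 0 yields three values. Sites could apply the range to the mean, to every value or to any value, and so admit different patients.
- **Baseline.** If one measurement both admits the patient and serves as baseline, patients are selected partly for a high reading on that day. Their IOP would be expected to fall later even with an inert device. With no control arm, the paired test and the 20% success rates count that fall as treatment effect.

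At stake are consistent entry among 25 patients and how much of the 6-month reduction can be credited to the implant.

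**Working it through.** **Inputs from the Synopsis.** Difference 5.2 mmHg, diluted to 0.75 × 5.2 = 3.9 for 25% dropout; SD of the difference 5.83 (from 3² + 5² = 34); two-sided alpha 0.05; power 0.90; N = 25, with 16 completers at 6 months; baseline 26.0 ± 3.0 mmHg; entry range 21-35 mmHg. The correlation r between repeat diurnal values is not given; 0.5 to 0.9 is assumed.

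**1. The plan's own figure.** Normal approximation: ((1.960 + 1.282) × 5.83 / 3.9)² = 23.5, so 24. Exact noncentral t gives 26 (power 0.894 at 25, 0.906 at 26). The stated 25 lies between them, and this point does not affect it.

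**2. The visit count.** Visits 0 to 10 make 11 columns. Ten visits fits Visit 0 plus nine follow-ups, leaving out surgery. It fits Visits 1 to 10 equally well, with Visit 0 uncounted. The count therefore does not settle how many pre-operative visits were meant.

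**3. Regression to the mean if 26.0 ± 3.0 is itself a truncated distribution.** A normal distribution cut at 21 and 35 that yields 26.0 ± 3.0 has an unselected mean of 25.00 and SD 3.86. If the diurnal mean qualifies at one visit and the device is inert, the expected fall is (1 − r) × (26.0 − 25.0). The model's own SD of the difference is √[(1 − r)² × 3.0² + (1 − r²) × 3.86²]. The last two columns give the chance of a significant reduction at n = 25, where 2.5% is nominal.

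| r | Fall (mmHg) | Model SD | Chance, model SD | Chance, SD 5.83 |
|---|---|---|---|---|
| 0.5 | 0.50 | 3.66 | 9.6% | 6.1% |
| 0.8 | 0.20 | 2.39 | 6.0% | 3.6% |
| 0.9 | 0.10 | 1.71 | 4.7% | 3.0% |

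The plan's 5.83 has no covariance term. It does not belong with an inert device and a positive correlation, so the model-SD column is the consistent one.

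**4. Sensitivity to the source.** A normal source of mean 24 and SD 5, cut at the same limits, gives 26.1 ± 3.3, close to the plan's baseline. The fall is (1 − r) × (26.09 − 24) = 1.05, 0.42 and 0.21 mmHg at r = 0.5, 0.8 and 0.9. A source of mean 18 and SD 5 gives 3.0 mmHg at r = 0.5, but its selected values are 24.1 ± 2.5, which does not match the plan's baseline.

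**5. Against the planned effect.** The 95% half-width at n = 25 is 2.064 × 5.83 / 5 = 2.41.

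- Around 5.2, the lower limit is 2.79.
- Around the diluted 3.9, it is 1.49.
- With 16 completers and 5.2, it is 5.2 − 2.131 × 5.83 / 4 = 2.09.

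All three exceed 1.05 mmHg.

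**6. What a second measurement would do.** If both visits must qualify, as the criterion literally reads, both are selected. Under the step 3 source the fall at r = 0.5 and 0.8 is 0.40 and 0.14 mmHg, against 0.50 and 0.20. If the second set does not gate entry, the bias vanishes only when the correlation is the same at all intervals. With 0.8 between pre-operative days and 0.65 to 0.5 at 6 months, 0.15 to 0.30 mmHg remains.

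**The case for a change.** The case for acting is that the contradiction needs no assumption, clarification costs little, and inconsistent entry is hard to repair with 25 patients. If within-day correlation is 0.9 to 0.7 and there is no clock-time pattern (both assumed), 15-28% of patients admitted when any reading qualifies would be refused when every reading must, or 4 to 7 of 25. If a second visit also had to qualify, 5-11% of those passing Visit 0 would fail it (r = 0.9 to 0.5, step 3 source).

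It stands that the passages do not agree and that the qualifying reading is not stated in the supplied text. Tidying the wording is reasonable, and the choice of rule is the sponsor's. But only the synopsis is available, and the full plan may define the reading. Nor does the mismatch stop a site from working: one diurnal set exists before surgery, and the range can be applied to it. The eligibility shares show that the readings of the rule differ. They do not show that sites would differ, or that the 6-month conclusion would change.

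It also stands that regression to the mean is present and uncontrolled. That belongs to a small single-arm device study and would be reduced, not removed, by rearranging the baseline.

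**Conclusion.** No change to the plan follows. The two-visit wording is best read as a clerical mismatch with the single Visit 0, and the unspecified reading as a detail the study team can settle from the one diurnal set scheduled.

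The shared qualifying and baseline measurement is a genuine caveat on attribution. Its size depends on a correlation and a source distribution that the documents do not give: about 0.1-0.5 mmHg (2-10% of 5.2) under the truncated-normal reading of 26.0 ± 3.0, and up to about 1.05 mmHg (20% of 5.2) under the other source close to the plan's baseline. Under the first reading, an inert device would show a significant reduction about 5-10% of the time instead of 2.5%. Neither figure accounts for a reduction of the planned size. The net bias also depends on medication changes by month 6.

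The one remedy that could alter a result, a separate baseline, cannot avoid selection if both visits must qualify. Otherwise it requires a different entry rule and a further three-reading day, and may remove only part of a modest bias. Writing a fixed bias range into the plan would give assumed figures a standing they lack. The reduction and the success rates should simply be read as uncontrolled before-and-after results.

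### The exclusion for anticipated study-eye surgery looks ahead 12 months, but IOP and endothelial cell density are assessed to 24 months, and the supplied text has no rule for values obtained after a later operation.

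*Combined protocol and SAP*

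**What the plan says.** - **Exclusion criteria (Synopsis, Patient selection).** An eye is ineligible if there is "Anticipated need for ocular surgery or retinal laser procedure in the study eye in the 12 months following surgery". The only criterion that names the lens concerns subluxation or luxation. Cataract and lens status are not mentioned.
- **Design.** "The procedure will be a stand-alone surgery", with one non-comparative cohort of 25. Patients "perform several examinations up to 24 months after surgery".
- **Primary objective.** It compares baseline with "medicated diurnal IOP at 6 months after surgery".
- **Secondary objectives.** One reads "To test the reduction in medicated diurnal IOP between screening/baseline visit and medicated diurnal IOP 12 months and 24 months after surgery". Another reads "To assess the rate of peripheral and central corneal endothelial cells density-loss" and gives no time point of its own. The complete and qualified success definitions rest on IOP level, percentage reduction and medication use. Neither has a clause on further surgery.
- **Flow chart (Table 1).** Diurnal IOP is measured at baseline and months 6, 12, 18 and 24. The row "Peripheral and central specular microscopy" has a baseline mark and four later marks, which fit the same visits. Medications and adverse events are recorded at every visit. No row covers ocular procedures performed after implantation.

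**The concern.** The plan limits the influence of other eye surgery in two ways: the implant is placed on its own, and eyes expected to need another procedure are kept out. The second safeguard ends a year before the last efficacy and safety visit. An eye with an operation foreseen for, say, month 14 is not barred by this criterion, yet its month-18 and month-24 values feed stated objectives.

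There is no control arm in which the effect of a second operation would also appear. If later surgery lowered IOP, the fall would be credited to the implant. If it cost endothelial cells, the loss would be charged to the implant. An eye whose IOP came down only after a second operation could also meet a success definition. The supplied text does not say how values after such surgery are analysed.

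**Working it through.** **1. The plan's own sample size, and whether this point touches it.** Inputs from the Sample Size section: paired t-test, two-sided alpha 0.05, power 0.90, difference 0.75 × 5.2 = 3.9 mmHg, SD = √(3² + 5²) = √34 = 5.83.

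- Normal approximation: n = ((1.96 + 1.28) × 5.83 / 3.9)² ≈ 23.5, so 24.
- Exact noncentral t: n = 26, with power 89.4% at n = 25. The stated 25 is reproduced to within one patient.
- Exact t with the undiluted 5.2 mmHg: n = 16, which matches the 16 completers sought at 6 months.

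All of this concerns month 6, inside the 12-month look-ahead. The exclusion horizon does not enter the calculation.

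**2. Look-ahead against visit windows** (flow chart; 12 months taken as 365 days).

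| Visit | Window (days) | Position relative to Day 365 |
|---|---|---|
| Month 6 | 168-196 | inside |
| Month 12 | 335-425 | may run up to 425 − 365 = 60 days past |
| Month 18 | 510-600 | at least 510 − 365 = 145 days past |
| Month 24 | 700-790 | at least 700 − 365 = 335 days past |

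The primary visit is covered. The month-12 visit is mostly covered. Months 18 and 24 are not.

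**3. Possible size.** The documents give no rate of later surgery and no effect of it, so every input here is an assumption. If k of n eyes are operated on in months 13-24 and each has an extra change s, the mean moves by (k/n) × s.

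| | n = 25 | n = 16 |
|---|---|---|
| IOP, k = 1, s = 1 mmHg | 1/25 × 1 = 0.04 | 1/16 × 1 = 0.06 |
| IOP, k = 5, s = 4 mmHg | 5/25 × 4 = 0.80 | 5/16 × 4 = 1.25 |
| Endothelial loss, k = 1, s = 5 points | 1/25 × 5 = 0.2 | 1/16 × 5 = 0.3 |
| Endothelial loss, k = 5, s = 15 points | 5/25 × 15 = 3.0 | 5/16 × 15 = 4.7 |

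Here k counts all surgery in months 13-24. Only the part already foreseen at screening is due to this criterion, so these figures are upper bounds on what a longer look-ahead could remove.

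**4. How likely is at least one such eye?** The chance is 1 − (1 − p)²⁵. For an assumed p of 2%, 5% or 10% per eye it is 40%, 72% or 93%.

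**5. Against the plan's own variability.** Assume the month-6 SD also holds at month 24. With 16 eyes the standard error is 5.83/√16 = 1.46 mmHg, so the largest IOP shift above is 1.25/1.46 = 0.86 standard errors. If an observed change of 5.2 mmHg contained that shift, 5.2 − 1.25 = 3.95 mmHg would remain, and t = 3.95/1.46 = 2.7. That is still significant at the two-sided 5% level.

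**6. Success rates.** One eye is 1/25 = 4% of the cohort, or 1/16 = 6.3% of 16 completers. One eye reclassified after a second operation moves the rate by that much.

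**The case against.** The strongest reply is that the criterion merely fails to bar these eyes. An investigator who expects surgery at month 14, but is confident that none is needed by month 12, is describing a narrow case. A 24-month forecast is also less certain and would cost some recruitment. No statement in the plan says that the criterion exists to isolate the implant effect. How far ahead it should look is an eligibility decision for the sponsor. On the figures above, the 24-month IOP test would be unlikely to reverse. Finally, the supplied document is a synopsis, and a fuller plan may contain a rule for later surgery.

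Much of this stands. A reader might infer that such eyes will enter and will bias the 24-month results. The documents show only that they may. A reader might also infer that cataract surgery is the specific problem. It is one plausible example, but the criterion covers any ocular surgery and cataract is never mentioned. Nor do the documents support carrying the concern over to the 6-month primary objective.

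The reply does not remove the mismatch between the two horizons, or the silence of the supplied text on values after later surgery. A longer look-ahead alone would not settle the second matter, because unforeseen operations would still occur.

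**Conclusion.** The point holds as a gap in protecting the 24-month secondary results. Eyes with foreseen surgery in months 13-24 may enter, and without a control arm or an analysis rule their later IOP and endothelial values could not be told apart from the device effect.

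The size is unknown. Under the assumed ranges the effect on mean IOP is modest unless several eyes are operated on. Mean endothelial loss and the success rates deserve at least as much attention, because each eye carries so much weight. These statements rest on assumed numbers of operated eyes, assumed effects per eye and, for the significance check, an SD carried over from month 6. The statement that no handling rule exists applies to the supplied synopsis only.

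**What to change.** 1. Reconcile the exclusion look-ahead with the 24-month objective, or state openly that the month-18 and month-24 results are not protected from later study-eye surgery. The choice of horizon is the sponsor's. A longer one is an edit to one criterion and may slow recruitment of the 25 slightly.
2. Record every study-eye ocular procedure through month 24, with date and reason. The flow chart has no such row, and elective surgery may not be captured reliably as an adverse event. This adds a small case-report-form item.
3. Pre-specify month-18 and month-24 IOP change and endothelial cell density in two forms: all values, and without values obtained after unrelated intraocular surgery. This costs one extra tabulation.
4. Do not drop eyes operated on for uncontrolled IOP or for implant revision or removal. Report them separately and count them as failures in the complete and qualified success rates. Removing values after any operation would take device failures out of the result and flatter it.

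### The pregnancy exclusion is fixed at screening, 1 to 42 days before implantation, and the synopsis schedules no re-confirmation of changeable exclusions before surgery

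*Combined protocol and SAP*

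**What the plan says.** The exclusion criteria in the Synopsis (Patient selection) open with the rule "Any patient is not eligible for inclusion in this clinical investigation if one or more of the following criteria apply". Two of the listed criteria describe states that can change within weeks:

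- Pregnancy: "Only for women of childbearing potential: positive urine pregnancy test at screening". The criterion carries its own time anchor.
- Eye infection or inflammation: "Clinically significant intra-ocular inflammation or infection, presence of ocular disease such as uveitis, ocular infection, severe dry eye, severe blepharitis", among others. This criterion has no time anchor.

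The table under Design places "patient inclusion" in the screening/baseline column. The flow chart (Table 1) gives Visit 0 a window of Day -42 to -1 and sets surgery (Visit 1) at Day 0. The rows "Inclusion /exclusion criteria" and "Urine pregnancy test (women of childbearing potential only") are each marked at Visit 0 and nowhere else. The row "Slit lamp examination" is marked at Visit 0, blank at Visit 1, and marked again from Visit 2.

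**The concern.** The exclusions protect the patient, and the interpretability of the safety data, at the moment of implantation. The plan applies them at another moment. If a patient's status changes in between, the recorded eligibility decision no longer describes the person who is operated on.

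Two things are at stake. The first is the safety of a woman whose pregnancy becomes detectable after Visit 0. The second is how cleanly the safety findings can be read. Adverse events and adverse device effects are secondary objectives, and there is no control group. For an eye that becomes inflamed shortly before surgery, the plan schedules no preoperative examination near Day 0 that would document its state before the implant.

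**Working it through.** **Length of the interval.** Inputs are the flow-chart windows: Visit 0 at Day -42 to -1, surgery at Day 0, Visit 2 at Day 1.

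- Shortest gap from eligibility check to implantation: 0 - (-1) = 1 day.
- Longest gap: 0 - (-42) = 42 days, or 6 weeks.
- Gap between the last scheduled slit-lamp examination before surgery and the first one after it: from 1 - (-1) = 2 days to 1 - (-42) = 43 days.

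**What is scheduled around surgery.** Reading the relevant flow-chart rows by column:

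| Row | Visit 0 | Visit 1 (surgery) | Visit 2 (Day 1) |
|---|---|---|---|
| Inclusion/exclusion check | marked | blank | blank |
| Urine pregnancy test | marked | blank | blank |
| Slit lamp | marked | blank | marked |
| Dilated fundus | marked | blank | marked |
| Eye symptoms | marked | blank | marked |
| Concomitant medications | marked | marked | marked |
| AE/SAE recording | marked | marked | marked |

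The other rows marked at Visit 1 are implantation, implant position, surgery video, ease-of-use questionnaire and gonioscopy image. None of these is an eligibility check. No text in the synopsis calls for eligibility to be confirmed again before implantation, or says what a new AE or medication recorded at Visit 1 means for eligibility.

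**What follows for each criterion.**

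1. *Pregnancy.* The criterion is met by a positive test at screening. A woman who is negative at Visit 0 and positive on, say, Day -3 has not met it. This follows from the wording alone, and the flow chart agrees with the wording because it schedules no later test.
2. *Infection or inflammation.* The criterion names no date. An eye with active uveitis on Day 0 meets it in plain words. The gap is that nothing is scheduled to find and act on that eye: there is no eligibility mark, slit lamp, fundus examination or symptom record between Visit 0 and implantation.

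**Effect on the efficacy analysis.** The sample-size inputs (difference of interest, dropout, standard deviation, alpha, power) do not depend on when eligibility is confirmed, so 25 patients and the planned power are unchanged.

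**The case against.** The strongest reply is that the plan is less exposed than the flow chart suggests. A reader might infer that any patient who meets a changeable exclusion on the day of surgery still qualifies. The documents do not support that. Where the drafters wanted a screening anchor they wrote one, as they did for pregnancy, systemic acetazolamide and prior laser trabeculoplasty. They wrote none for infection and inflammation. A further exclusion covers ocular or systemic pathology that the physician expects to complicate recovery from implantation. It also has no screening anchor, it looks forward to surgery, and it could cover a newly inflamed eye. Medications and AEs are recorded at Visit 1, so a new infection has a place to surface. All of this stands, and it limits the wording problem to pregnancy. It does not supply a scheduled check, and the text links neither record to eligibility.

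A reader might also infer that inflammation present before surgery would be counted as a device effect. The documents do not say so. AEs are recorded from Visit 0, so an onset before surgery could already be on file, and the secondary objectives list AEs separately from adverse device effects. Misattribution is possible only where the onset went unnoticed.

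Third, one affected eye would be 1/25 = 4% of the cohort, but that is the weight of one patient, not a probability. The documents give no event rate, no number of women of childbearing potential and no typical screening interval.

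Fourth, the criterion and the flow chart agree with each other on pregnancy, so this is not an internal contradiction, and a very early pregnancy could be missed by a Day 0 urine test as well. Both points are fair. The mismatch is between the time of judgement and the time of exposure, and a later test shortens the blind interval without removing it.

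Finally, the available document is a synopsis. A fuller plan may contain a surgery-day check that cannot be seen here.

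**Conclusion.** The point holds in a limited form, as a low-cost improvement. For pregnancy the gap lies in the rule itself: the exclusion is settled at Visit 0, 1 to 42 days before implantation, and a later positive status is not excluded as written. For exclusions without a time anchor the rule is sound, but the synopsis schedules no step to apply it before implantation, so detection rests on AE and medication recording and the surgeon's judgement.

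The effect on the primary endpoint, sample size and power is nil. The number of patients affected cannot be estimated from the documents; 42 days is the maximum of the window and not a typical interval. The conclusion assumes that the flow-chart marks are complete and that no check exists in a fuller plan.

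**What to change.** Reconcile the time at which eligibility is judged with the time of exposure.

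- In the inclusion/exclusion row of the flow chart, add a mark at Visit 1, before implantation, with a note that it re-confirms the criteria that can change.
- Align the time anchor of the pregnancy criterion, and the pregnancy-test row, with that re-confirmation.
- If a fuller plan already contains such a check, refer to it in the flow chart.

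The cost is a few words, one or two flow-chart marks, a repeat dipstick for a few women, and an occasional late screen failure. No statistical section needs to change.
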